6. PROCEDURES

As of 05 Jul 2018, enrollment of new subjects into Phase 1 has been discontinued, and Phase 2 will not proceed. Subjects already enrolled who are receiving clinical benefit in the opinion of the treating investigator may continue to receive study treatment up to a maximum of 24 cycles of CC-122.

The screening period begins on the date the Informed Consent Document (ICD) is signed and will last for up to 28 days. The ICD must be obtained prior to beginning any assessments solely for the purpose of this study. Standard of care assessments performed prior to signing the ICD (as described in the protocol) may be used for this study, assuming they meet the protocol requirements and following discussion with the sponsor's medical monitor. Recording of AEs/serious adverse events (SAEs) will begin once the subject has signed the ICD. All prior anticancer treatments (eg, chemotherapy, surgeries) and medical history, including approximate dates of treatment or diagnosis, must be recorded during screening.

All study-required procedures should be performed as outlined in [Table 3](#) through [Table 5](#), depending on the arm to which the subject is assigned:

Table	Arm
Table 3	Arm A: CC-122 single agent with intrasubject dose escalation
Table 4	Arm B: CC-122 in combination with ibrutinib
Table 5	Arm C: CC-122 in combination with obinutuzumab

As of Protocol Amendment 7, some clinic visits and assessments may be omitted as noted in [Table 3](#) through [Table 5](#), and in Section 6.6 below.

Excursions from the timing of assessments will be considered protocol deviations and should be recorded in the source document along with the reason for the excursion.

All scheduled laboratory assessments are to be performed at the designated central laboratory. However, local laboratories may be used for the biweekly assessments (Days 8 and 22) during the third cycle of CC-122 dosing, and for decisions affecting treatment and dose modifications. For subjects on Arm A who dose escalate every 2 weeks, local laboratories may be used however the designated central laboratory is recommended.

All laboratory values should be carefully monitored, especially following the initial treatment, throughout the first two cycles and for dose escalations of CC-122. Serum creatinine and creatinine clearance, uric acid, phosphorus, calcium, and potassium labs should be monitored closely on Days 1, 2, 4, and 8 during the first cycle of CC-122 (ie, Cycle 1 in Arms A and C) and (Cycle 2 in Arm B) [REDACTED] and unscheduled assessments performed as needed.

6.1. Safety Assessments

Study safety evaluations will occur in accordance with [Table 3](#) through [Table 5](#), and should be performed in accordance with this section of the protocol. The safety of CC-122 single agent

and CC-122 in combination with ibrutinib and in combination with obinutuzumab will be assessed using AEs, physical examinations (PEs), concomitant medications and procedures, clinical laboratory tests, vital signs, electrocardiograms (ECGs), and an echocardiogram/multi-gated acquisition scan (MUGA).

Detailed procedures for obtaining each assessment are provided below.

6.1.1. Demographics / Medical History / Baseline Stage and Prognostic Classification

Demographics (gender, race, ethnicity, and date of birth), medical history, and the Cumulative Illness Rating Scale (CIRS) Score ([Appendix G](#)) will be documented by a qualified clinician at the time of the Screening visit. The medical history will be general enough to document common comorbid conditions as well as specific enough to reveal any conditions listed as participation exclusion criteria, and will document whether the identified conditions are active or inactive at the time of enrollment. The CIRS score will be collected to assess the performance status and fitness of subjects.

6.1.1.1. Prognostic Classification

Chronic lymphocytic leukemia-specific international prognostic classification reflecting the subject's status at the time of enrollment will be documented

6.1.2. Adverse Events

All subjects will be evaluated for AEs during all scheduled visits starting at the signing of the ICD until 28 days after the last dose of study treatment.

6.1.3. Vital Signs

Vital sign measurements will be obtained at each visit as indicated in [Table 3](#) through [Table 5](#). These assessments include systolic and diastolic blood pressure, heart rate, respiration rate, body temperature and body weight. Measurements of height will be recorded only at the Screening visit.

Vital signs should be measured after the subject has rested for at least 5 minutes. Vital sign measurements should be repeated for confirmation if clinically significant observations or changes from baseline occur. All confirmed, clinically significant vital sign measurements must be recorded as an AE.

After the first 12 cycles of CC-122, in the absence of Grade ≥ 2 adverse events related to CC-122, and as clinically indicated, some clinic visits and assessments may become less frequent as detailed in Section [6.6](#).

6.1.4. Physical Examination

Complete PEs, including evaluation of lymph nodes, spleen and liver will be performed during Screening, on Cycle 1 Day 1 and will continue to be performed on Day 1 of each subsequent treatment cycle under Protocol Amendment 7 as part of the assessment for response (in the absence of imaging), at the EOT visit and at 28 days after the last IP discontinuation.

Measurements of lymph nodes and documentation of any enlargement of the spleen and/or liver should be recorded in the source document and eCRF.

Symptom driven limited PEs will be performed as clinically indicated at any study visit.

6.1.5. Cardiac Laboratory Testing

Subjects will undergo laboratory monitoring of plasma troponin-T and B-type natriuretic peptide (BNP) to evaluate for potential early evidence of cardiac toxicity. Testing will be performed at Screening, weekly during the first cycle of CC-122 treatment and for the first cycle of each dose escalation (Days 1, 8, 15, and 22), Day 1 of each subsequent cycle, and at the EOT visit. A significant elevation of troponin-T is defined as a value greater than the upper limit of normal (ULN) for the assay with associated elevation of BNP or other significant cardiac symptoms or findings. A significant elevation of BNP is defined as a $\geq 20\%$ increase over baseline with an absolute value > 100 pg/mL. Subjects who are found at Screening to have baseline troponin-T $>$ ULN or BNP > 100 pg/mL must have a baseline evaluation by a cardiologist during screening to optimize cardioprotective therapy.

After the first 12 cycles of CC-122, in the absence of Grade ≥ 2 adverse events related to CC-122, and as clinically indicated, some clinic visits and assessments may become less frequent as detailed in Section [6.6](#).

6.1.6. 12-Lead Electrocardiogram

TriPLICATE or single standard 12-lead ECGs will be recorded at the visits listed in [Table 3](#) through [Table 5](#). The 12-lead ECGs (12-lead at 25 mm/sec reporting rhythm, ventricular rate, PR-interval, QRS complex, QT interval, and QTc interval) will be performed after the subject has been in the supine position for at least 5 minutes.

TriPLICATE ECGs (3 recordings within 2 ± 1 minute intervals) will be performed at Screening for all subjects. In addition, triplicate ECGs will be collected as follows:

Arm A: Cycle 1 Day 1: 0 and 1.5 hours (± 15 minutes) after CC-122 dosing

Arm B: Cycle 1 Day 1: 0 and 1.5 hours (± 15 minutes) after ibrutinib dosing
Cycle 2 Day 1: 0 and 1.5 hours (± 15 minutes) after CC-122 dosing
Cycle 2 Day 15: 0 and 1.5 hours (± 15 minutes) after CC-122 dosing

Arm C: Cycle 1 Day 1: 0 and 1.5 hours (± 15 minutes) after obinutuzumab dosing
Cycle 1 Day 9 and Cycle 1 Day 23: 0 and 1.5 hours (± 15 minutes) after CC-122 dosing

A single ECG will be performed on all other visits where an ECG is indicated per [Table 3](#) through [Table 5](#) approximately 1.5 hours (± 15 minutes) after dosing.

After the first 12 cycles of CC-122, in the absence of Grade ≥ 2 adverse events related to CC-122, and as clinically indicated, some clinic visits and assessments may become less frequent as detailed in Section [6.6](#).

6.1.7. Left Ventricular Ejection Fraction

Left ventricular ejection fraction (LVEF) MUGA, or echocardiogram (ECHO) will be conducted at Screening, after the first cycle of CC-122, and every 3 cycles thereafter (± 7 days), and at the EOT if not performed within the previous 8 weeks.

After the first 12 cycles of CC-122, in the absence of Grade ≥ 2 adverse events related to CC-122, and as clinically indicated, some clinic visits and assessments may become less frequent as detailed in Section [6.6](#).

6.1.8. Clinical Laboratory Tests

The following laboratory assessments will be performed at the Screening visit and during the study at the time points as described in [Table 3](#) through [Table 5](#). All samples will be analyzed at a central laboratory unless otherwise specified. All samples should be drawn predose unless otherwise specified. Laboratory assessments will be recorded in the source document and eCRF:

- Amylase, lipase, fasting lipid profile, creatine kinase, thyroid-stimulating hormone (TSH), free T4 (FT4), immunoglobulins (IgG, IgM and IgA only), T-cell subsets
- CBC: hemoglobin, hematocrit, red blood cell count with indices, white blood cell count with absolute differential and platelet count.
- Serum chemistry: albumin, total protein, bicarbonate, calcium, phosphorus, serum creatinine, serum urea/blood urea nitrogen (BUN), glucose (fasting), potassium, sodium, magnesium, chloride, total bilirubin, alkaline phosphatase, aspartate aminotransferase (AST or serum glutamic oxaloacetic transaminase [SGOT]), alanine aminotransferase (ALT or serum glutamate pyruvic transaminase [SGPT]), and lactate dehydrogenase (LDH) and uric acid.
- Beta-2 Microglobulin

- C-reactive protein
- Direct antiglobulin test (local laboratory only)
- Coagulation tests: prothrombin time, international normalized ratio, and partial thromboplastin time
- Urinalysis: dipstick, with microscopy in event of positive (1+ or greater) blood or protein and 24-hour collection for creatinine clearance and protein quantification in the event of 2+ or greater protein.
- Virus Serology: hepatitis B antigen (HBsAg), hepatitis B core antibody (anti-HBc), and hepatitis C virus (HCV) RNA

After the first 12 cycles of CC-122, in the absence of Grade ≥ 2 adverse events related to CC-122, and as clinically indicated, some clinic visits and assessments may become less frequent as detailed in Section 6.6.

6.1.9. Prior/Concomitant Medications and Procedures

All subjects will be evaluated for any concomitant medications and procedures during all scheduled visits from the signing of the ICD until 28 days after the last dose of study treatment.

6.1.12. Ophthalmologic Examinations

An ophthalmologic examination will be performed by a qualified ophthalmologist at Screening as described below in all subjects. The Screening ophthalmologic exam will include:

- Visual acuity
- Slit-lamp examination with fluorescein staining following pupillary dilation (unless fluorescein and pupillary dilatation are contraindicated)

- Ophthalmologic examination focusing on the anterior chamber, iris and anterior vitreous

Subsequent ophthalmologic examinations will be performed as clinically indicated. If there are any clinically significant findings, a full ophthalmologic exam will be conducted by a qualified ophthalmologist.

6.1.13. Contraceptive and Risk Counseling

Subjects will be counseled about appropriate contraception during Screening. Complete abstinence or double contraceptive methods (one of which must be a barrier method) for females (eg, oral, injectable, or implantable hormonal contraceptive; intra-uterine device; barrier contraceptive with spermicide; or vasectomized partner) must be used from the time ICF is signed, throughout the study and for 28 days after the last dose of CC-122. A single contraceptive method for males (complete abstinence or a condom) must be used from the time the ICF is signed, throughout the study, and for 3 months after the last dose of CC-122. Counseling should be documented in source documents.

The CC-122 Pregnancy Risk Minimization Plan for Celgene Clinical Trials ([Appendix F](#)) applies to all subjects receiving CC-122 therapy and will be given to sites as a separate document.

CC-122 will be dispensed through a qualified healthcare professional (including but not limited to nurses, pharmacists and physicians). These healthcare professionals will be trained by Celgene, or designee, in requirements specific to counseling of subjects.

Once trained, these healthcare staff will counsel subjects prior to the administration of CC-122 to ensure that the subject has complied with all requirements including use of birth control and that the subject understands the risks associated with CC-122. This step will be documented with a completed Education and Counseling Guidance Document, and CC-122 will not be administered until this step occurs.

A CC-122 Information Sheet will be provided to each subject before IP is dispensed.

Females of childbearing potential and males, other than the subject, should not handle or administer CC-122 unless they are wearing gloves.

Arm C: Females of childbearing potential should use effective contraception during obinutuzumab treatment and for 18 months following obinutuzumab therapy ([GAZYVA](#), [GAZYVARO](#)).

Arm B: Females of childbearing potential should avoid becoming pregnant while taking ibrutinib because ibrutinib can cause fetal harm ([IMBRUVICA](#)).

6.1.14. Pregnancy Test

A female of child bearing potential (FCBP) is defined as a sexually mature woman who has:

1. Not undergone a hysterectomy or bilateral oophorectomy, and
2. Not been naturally postmenopausal (amenorrhea following cancer therapy does not rule out childbearing potential) for at least 24 consecutive months (ie, has had menses at any time in the preceding 24 consecutive months).

The investigator will classify a female subject as a FCBP according to this definition. Pregnancy testing is not required for non-FCBP subjects but justification must be recorded in the eCRF and the source document. Pregnancy testing will be conducted by the local laboratory.

For a FCBP, pregnancy testing will be conducted at the visits listed in [Table 3](#) through [Table 5](#):

- A serum pregnancy test with sensitivity of at least 25 mIU/mL is to be obtained at Screening.
- A serum or urine pregnancy test (based on investigator's discretion and minimum test sensitivity [25 mIU/mL]) should be done weekly for the first cycle, within 72 hours prior to Day 1 of every cycle (with the exception of the first day of CC-122 dosing on which it must be performed within 24 hours of first dose), EOT visit and 28 days post IP discontinuation.
- The subject may not receive IP until the investigator has verified the Screening pregnancy tests to be negative.
- A FCBP must avoid activities that could lead to conception for 28 days after the last dose of CC-122 or a male subject whose partner is an FCBP must avoid activities that could lead to conception for 3 months after the last dose of CC-122.
- Please refer to the ibrutinib and the obinutuzumab PI(s) or SmPC(s) for additional recommendations.

Note: FCBP receiving CC-122 will undergo pregnancy testing according to the schedule described in the CC-122 Pregnancy Prevention Risk Management Plan (PPRMP) and CC-122 Information Sheet.

Results for pregnancy tests will be recorded in the source document and eCRF.

6.2. Efficacy Assessments

6.2.1. Efficacy Parameters

The following efficacy assessments will be performed at scheduled intervals throughout the study as described in [Table 3](#) through [Table 5](#).

6.2.2. Tumor Imaging Assessment

Tumor imaging assessment by CT scan is mandatory at Screening (neck, chest, abdomen, and pelvis), and after the first 6 cycles of CC-122 dosing [the 2nd scan is mandatory only for the affected regions with abnormal findings at baseline; Week 25 (for subjects on Arms A and C) or Week 29 (for subjects on Arm B), +4 weeks/-1 week], and is recommended if the subject discontinues study treatment due to an adverse event (if the subject shows signs of preliminary efficacy). Additional CT scan(s) is allowed if clinically indicated until documented disease progression or initiation of subsequent CLL therapy. The unscheduled CT scan(s) should be documented in the CRF. A CT scan with contrast is the recommended imaging modality. MRI may be used only if CT with contrast is medically contraindicated or if the frequency of CT scans exceeds local standards. Standard of care CT scans or MRI performed up to 56 days prior to Cycle 1 Day 1 may be acceptable for Screening, even if performed prior to signing the ICD. All imaging assessments will be evaluated by a reader at the local institution.

6.2.3. Bone Marrow Examination

A bone marrow aspirate and biopsy are optional for all subjects at Screening. A bone marrow aspirate and biopsy must be collected for all subjects at the time of the CR/CRi confirmation visit within 12 weeks after clinical, imaging, and laboratory response criteria have been met.

6.2.4. Minimal Residual Disease (MRD) Assessment

Peripheral blood for MRD assessment should be collected during Screening, every 6 cycles (only if subject is receiving CC-122, up to a maximum of 24 cycles), and at the time of CR/CRi confirmation visit (within 12 weeks after clinical and laboratory response criteria have been met). For those subjects found to be MRD positive in the peripheral blood at the CR/CRi confirmation visit, a peripheral blood sample for MRD assessment should be collected approximately every 6 cycles thereafter until MRD negativity is achieved or relapse/progression is documented. Peripheral blood for MRD assessment should also be collected at the time of PR (within 12 weeks after clinical, imaging, and laboratory response criteria have been met). A bone marrow aspirate for MRD assessment should be collected at the time of CR/CRi confirmation visit and once MRD-negativity is achieved in peripheral blood unless MRD negativity in bone marrow was documented earlier. Peripheral blood for MRD assessment should also be collected at the time of relapse/progression in subjects who previously achieved MRD negativity in peripheral blood.

MRD analyses will be performed by a central laboratory.

[figure not shown]

[figure not shown]

Thereafter, the minimum frequency of visits is once monthly (until the first 12 cycles of CC-122 have been completed, see Section 6.6) and appropriate procedures/tests are expected to be performed. Note that the drug dispensed at a given visit should cover the anticipated time to the next scheduled visit. Owing to the requirements of the PPRMP and its proscriptions concerning the availability of drug and the importance of pregnancy testing and counseling, a subject must visit with a minimum frequency of every 28 days.

6.6. Phase 1 Dose Escalation - Cycle 13 of CC-122 and Beyond

Beginning with Cycle 13 of CC-122, the following Day 1 clinic visits and assessments may be performed on a less frequent schedule at the discretion of the investigator in the absence of any Grade ≥ 2 toxicity related to CC-122.

- **Tests to occur every cycle (can be up to 7 days prior to Day 1) in order for CC-122 to be dispensed:**
 - Serum or urine pregnancy test in females of childbearing potential as per CC-122 PPRMP ([Appendix F](#), Section 19).
 - CC-122 Contraceptive and Risk Counseling and Education ([Appendix F](#), Section 19).
 - Hematology: CBC with differential and platelet counts.
 - Laboratory test may be performed up to 48 hours before the visit.
 - Physical Examination.
 - Recording of adverse events:
 - Subjects will be queried on any new adverse events that were experienced by the subject and recorded in the source documents and CRFs.
 - Recording of concomitant medications and procedures
- **Tests to occur every 1-3 months (\pm 7 days) in the absence of any Grade \geq 2 toxicity related to CC-122:**
 - Vital signs and weight
 - [REDACTED]
 - Laboratory tests (may be performed up to 48 hours before the visit):
 - Serum chemistries: albumin, total protein, bicarbonate, calcium, phosphorus, serum creatinine, serum urea/BUN, glucose (fasting), potassium, sodium, magnesium, chloride, total bilirubin, alkaline phosphatase, AST, ALT, LDH, and uric acid
 - C-Reactive Protein
 - Cardiac-specific troponin-T, BNP
 - PT/INR/PTT
 - Amylase, lipase, fasting lipid profile, creatine kinase, TSH, FT4, immunoglobulins
 - Urinalysis with microscopy
 - [REDACTED]
 - 12-lead single ECG (3 recordings within 2 ± 2 minute intervals) will be performed both at predose (within 90 minutes prior to dosing) and at 1.5 hours post dose
 - LVEF by ECHO or MUGA only if clinically indicated
 - T-cell subsets should continue to be obtained on Day 1 of each cycle

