 - o For Arm C, subjects must agree to use adequate contraceptive methods for 18 months (please refer to the obinutuzumab IB, PI, and SmPC).
 - Complete abstinence is only acceptable in cases where this is the preferred and usual lifestyle of the subject.
 - Periodic abstinence (calendar ovulation, symptothermal, post-ovulation methods) and withdrawal **are not acceptable**.
- c. Males (including those who have had a vasectomy) must practice complete abstinence or use barrier contraception (condoms) when engaging in sexual activity with FCBP as specified in the PPRMP.
- d. Males must agree not to donate semen or sperm for the duration of the study and for 3 months after the last dose of CC-122.
- e. All subjects must:
 - Understand that the IP could have a potential teratogenic risk.

- Agree to abstain from donating blood while taking IP and following discontinuation of IP.
- Agree not to share IP with another person.
- f. Other than the subject, FCBP and males should not handle the IP or touch the capsules, unless gloves are worn.
- g. Be counseled about pregnancy precautions and risks of fetal exposure (see Section 6.1.13).

Arm B only:

10. Enrollment into Arm B will be permitted if ibrutinib is considered the standard of care in the clinical practice.

Expansion Cohort 2 of Arm C:

11. Subjects in Cohort 2 of Arm C must meet the following criteria:

- a. Subject must have received at least one BCR PI (ibrutinib, idelalisib, or other approved BTK or PI3K inhibitor) and/or venetoclax;
- b. Subject must be either resistant to or intolerant of (ie., treatment failures) the last BCR PI and/or venetoclax. Resistant is defined as relapsed or refractory per IWCLL2008:
 - i. Relapse is defined as a patient who has previously achieved a CR or PR, but after a period of 6 or more months, demonstrates evidence of disease progression.
 - ii. Refractory is defined as failing to achieve a CR or PR, or disease progression within 6 months after initiation of treatment with an approved BTK or PI3K inhibitor (eg, ibrutinib, idelalisib) or venetoclax.
 - iii. Intolerance is defined as the inability to continue treatment with a BCR PI or venetoclax due to toxicities or due to development of a contraindication that makes the subject ineligible to receive further treatment with a BCR PI or venetoclax.

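### Minor: from CC-122 Cycle 13 the Section 6.6 heading lets the pregnancy test be up to 7 days old, looser than the 72-hour window in Section 6.1.14 that appears to govern

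*Protocol*

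**What the plan says.** Protocol Section 6.6 applies from the thirteenth cycle of CC-122. It lets some Day 1 visits and assessments become less frequent when there is no CC-122-related toxicity of Grade 2 or higher. Its first group stays on an every-cycle schedule, under the heading "Tests to occur every cycle (can be up to 7 days prior to Day 1) in order for CC-122 to be dispensed". The group covers the pregnancy test, contraceptive counseling, blood count, physical examination, adverse events and concomitant medications. The pregnancy item comes first: "Serum or urine pregnancy test in females of childbearing potential as per CC-122 PPRMP", with a reference to Appendix F.

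Protocol Section 6.1.14 says a serum or urine test should be done weekly in the first cycle and "within 72 hours prior to Day 1 of every cycle (with the exception of the first day of CC-122 dosing"; on that first dosing day the limit is 24 hours. A note at the end adds: "FCBP receiving CC-122 will undergo pregnancy testing according to the schedule described in the CC-122 Pregnancy Prevention Risk Management Plan".

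The pregnancy-test row in Tables 3, 4 and 5 names the PPRMP and refers the reader to Section 6.1.14. It is marked in the open-ended late-cycle column of each table: Cycle 4 onward in Arms A and C, Cycle 5 onward in Arm B.

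**The concern.** Two sections print different limits for the same test, and the looser one stands in the section a site would open for a subject at Cycle 13 or later. Amendment 7 was issued to guide procedures for subjects remaining on treatment, who may receive up to 24 cycles of CC-122, so Section 6.6 is working text. A site that schedules the whole every-cycle list 5 or 6 days ahead of Day 1 would satisfy the heading and miss the 72-hour window.

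The test is one of the conditions for dispensing. Inclusion criterion 9.e requires subjects to "Understand that the IP could have a potential teratogenic risk". A longer gap between test and dispensing leaves more time for a conception that the test would not detect. There is also a compliance side: Section 6 treats excursions from assessment timing as protocol deviations, so sites need one clear limit.

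**Working it through.** The plan states no figure to reproduce, so the check is a comparison of texts with one conversion.

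**Inputs**
- Section 6.6 heading: up to 7 days before Day 1.
- Section 6.1.14: within 72 hours before Day 1 of every cycle; 24 hours for the first CC-122 dosing day, which is irrelevant by Cycle 13.

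**Arithmetic**
- 7 days × 24 = 168 hours.
- 168 − 72 = 96 hours, and 96 ÷ 24 = 4 days.

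| Age of test before Day 1 | Section 6.6 heading | Section 6.1.14 |
|---|---|---|
| 0 to 72 h | met | met |
| over 72 h, up to 168 h | met | missed |
| over 168 h | missed | missed |

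Only the middle row matters. A site that tests within 72 hours complies with both sections.

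**Which window does the visible text favor?**
1. The late-cycle columns of Tables 3 to 5 include Cycle 13 onward. Section 6 says procedures should follow those tables, and their pregnancy row leads to Section 6.1.14 and the PPRMP. This favors 72 hours.
2. Sections 6.1.3 and 6.1.5 to 6.1.8 each say that assessments may become less frequent after 12 cycles, as set out in Section 6.6. Section 6.1.14 has no such sentence, so it does not yield to 6.6. (That sentence concerns frequency, not windows, in any case.)
3. The 6.6 pregnancy item has its own qualifier, the PPRMP, as does the note in 6.1.14. A qualifier on one item would normally limit a general heading over a mixed list.

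**Lines that do not settle it**
- Section 6.6 also prints "Laboratory test may be performed up to 48 hours before the visit". It follows the blood-count item and counts back from the visit, not from Day 1, so it does not fix the age of a pregnancy test at Day 1.
- Section 6 says that under Amendment 7 "some clinic visits and assessments may be omitted as noted in" Tables 3 to 5 and Section 6.6. That concerns omission, not timing.

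**The case against.** The strongest reply is that nothing is really in conflict. The 7-day phrase is a permissive outer bound over a mixed list, the pregnancy item carries its own reference to the PPRMP, and the tables send the site to Section 6.1.14. Section 6.1.13 says the plan in Appendix F goes to sites as a separate document, and criterion 9.a ties testing frequency to it. On this view sites held the controlling schedule, and the heading is loose drafting.

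Most of that stands. A reader might infer that the protocol leaves sites with two windows of equal rank, or that it deliberately relaxed pregnancy testing after Cycle 12. The documents support neither: the table rows, the PPRMP qualifier and the absence of any deference to 6.6 all point to Section 6.1.14. Nor can one conclude that a test taken 4 to 7 days ahead was an actual deviation, or that any subject was dosed on such a test. The first depends on the PPRMP and the table footnotes, which were not available here and whose absence is not a fault of the plan. The second depends on data the documents do not contain.

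What survives is narrow. The heading, as printed, covers the pregnancy item and permits a test older than 72 hours for dispensing, and no sentence exempts it. The PPRMP cannot agree with both printed limits: whatever single limit it sets, at least one of 7 days and 72 hours differs from it.

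**Conclusion.** The point holds as a minor inconsistency. The 72-hour window of Section 6.1.14, together with the PPRMP, appears to govern, and the error is that the 7-day heading in Section 6.6 extends to the pregnancy test. The excess is 96 hours, and only tests taken more than 72 and up to 168 hours before Day 1 are affected.

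This rests on reading the table cross-reference as controlling for late cycles, and on the unseen PPRMP and footnotes not saying otherwise. Confidence in which window prevails is therefore moderate; that the two printed limits differ is certain.

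The consequence is small. The test remains due every cycle, contraception and counseling continue, and enrollment is closed. Only females of childbearing potential still on CC-122 at Cycle 13 or later are concerned; their number is not given and may be zero. No endpoint, analysis population or sample size is affected.

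**What to change.** In Section 6.6, take the pregnancy test out of the 7-day allowance and write: *pregnancy test within 72 hours before Day 1 per Section 6.1.14 and the PPRMP*. Confirm the window against the PPRMP and the footnotes to Tables 3 to 5 first. If the PPRMP sets a different limit, state that one limit in both 6.1.14 and 6.6.

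The cost is one line in an amendment or site letter. No test is added: it is already required each cycle, may be serum or urine, and Section 6.1.14 says "Pregnancy testing will be conducted by the local laboratory", which makes retiming feasible. The drawback falls on a site that holds the whole every-cycle visit 4 to 7 days before Day 1. It would have to move the visit or arrange the pregnancy test separately, nearer to Day 1.
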